4.5. Region of Pooled Countries

The countries will be pooled to 2 regions as presented in [Table 2](#) for the analysis.

Table 2: The Region of Pooled Countries

Region	Country
United States	United States
Europe	Belgium, Czech Republic, Denmark, Finland, France, Germany, Italy, Netherlands, Poland, Spain, Sweden, Switzerland, United Kingdom

5. STUDY POPULATION

5.1. General

The ITT analysis set will be used for all study population summaries unless otherwise specified. Summaries will be presented by migraine classification (ie, CM, EM, and all), treatment group, all fremanezumab, and for all patients (ie, total).

For continuous variables, descriptive statistics (n, mean, SD, SE, median, minimum, and maximum) will be provided. For categorical variables, patient counts and percentages will be provided. Categories for missing data will be presented if necessary.

5.2. Patient Disposition

Patients screened, patients screened but not randomized, and the reasons the patients were not randomized will be summarized only for the overall group using patient counts.

Patients in the ITT analysis set, patients in the ITT analysis set but not treated, patients in the double-blind safety analysis set, double-blind mITT analysis set, and per-protocol analysis set, patients who complete the double-blind treatment period, patients who withdraw from the double-blind treatment period, patients in the open-label safety analysis set and open-label mITT analysis set, patients who complete treatment, patients who withdraw from treatment, patients who complete the study, and patients who withdraw from the study will be summarized using descriptive statistics. Patients who withdraw from treatment and patients who withdraw from the study will also be summarized using descriptive statistics by reason for withdrawal. The denominator for calculating the percentages will be the number of patients in the ITT analysis set.

5.3. Demographics and Baseline Characteristics

Patient demographics and baseline characteristics (age, weight, height, body mass index [BMI], time since initial migraine diagnosis [years], migraine classification [ie, CM or EM] as randomized and as per CRF, country, region, classes of migraine preventive medications that the patients have failed in the past 10 years, special group of treatment failure [ie, patients who must have had inadequate response to valproic acid and must have had inadequate response to 2 to 3 other classes of migraine preventive medications] as randomized and as per CRF, patients who over used acute medication, patients who failed 2, 3, and 4 classes of preventive medications including or not including valproic acid, and any triptans/ergots during baseline) will be summarized.

The baseline electronic headache diary efficacy variables and the other efficacy baseline values listed in Section 4.2 will be summarized.

Treatment groups will be compared for all continuous variables, using an analysis of variance (ANOVA) with treatment group as a factor. Treatment groups will be compared for all categorical variables using a Pearson's chi-square test (or Fisher's exact test if cell sizes are too small).

5.4. Medical History

All medical history will be coded using the Medical Dictionary for Regulatory Activities (MedDRA). The incidence of medical history abnormalities will be summarized using descriptive statistics by system organ class (SOC) and preferred term (PT). Patients are counted only once in each SOC and only once in each PT.

5.5. Prior Therapy and Medication

Any prior therapy, medication, or procedure a patient has had within 6 months before study drug administration will be recorded on the CRF. The sponsor will encode all therapy and medication according to the World Health Organization (WHO) drug dictionary (WHO Drug).

The incidence of prior therapies and medications will be summarized using descriptive statistics by therapeutic class and preferred term. Patients are counted only once in each therapeutic class category, and only once in each preferred term category. Prior therapies and medications will include all medications taken and therapies administered prior to the 1st study drug administration.

The subset of prior medications will be summarized for the following categories:

- migraine/headache preventive medication
- triptans and ergots for migraine/headache
- triptans and ergots for reasons other than migraine/headache
- butalbital for migraine/headache
- butalbital for reasons other than migraine/headache
- non-steroidal anti-inflammatory drugs (NSAIDs) for migraine/headache
- NSAIDs for reasons other than migraine/headache
- opioids for migraine/headache
- opioids for reasons other than migraine/headache
- preventive medication for other reasons

Past preventive headache/migraine medication use will be listed.

5.6. Childbearing Potential and Methods of Contraception

For female patients, information related to childbearing potential and menopause will be collected at screening. Data will be listed.

5.7. Study Protocol Deviations

Data from patients with any important protocol deviations during the study will be summarized overall and for each category using descriptive statistics.

6. EFFICACY ANALYSIS

6.1. General

The efficacy data for this study consist of headache related question responses (e.g., occurrence of headache, duration of headache in each day, maximum severity of headache, and acute migraine - specific medication use) collected daily using an electronic headache diary device.

In addition, the following questionnaires will be used for the assessments of migraine impairment, quality of life, and satisfaction of treatment etc. during the study.

- migraine-related disability using the HIT-6 (see [Appendix C](#))
- migraine-related disability using the MIDAS (see [Appendix D](#))
- migraine-specific quality of life, as measured by the MSQOL questionnaire (see [Appendix E](#))
- health status, as measured by the EQ-5D-5L questionnaire (see [Appendix G](#))
- patient depression status, as measured by the PHQ-2 and the PHQ-9 (see [Appendix H](#))
- patient work productivity and activity impairment, as measured by the WPAI questionnaire (see [Appendix I](#))
- assessment of patient satisfaction, as measured by the PGIC scale (see [Appendix J](#))

For the purpose of this study, a migraine day is endorsed when at least one of the following occurs:

- a calendar day (0:00 to 23:59) demonstrating at least 4 consecutive hours of a headache, meeting criteria for migraine with or without aura (Appendix U in protocol)
- a calendar day (0:00 to 23:59) demonstrating least 4 consecutive hours of a headache meeting criteria for probable migraine, a migraine subtype where only 1 migraine criterion is missing (Appendix U in protocol)
- a calendar day (0:00 to 23:59) demonstrating a headache of any duration that was treated with migraine- specific acute medications (triptans and ergot compounds)

A headache day of at least moderate severity is endorsed when at least 1 of the following situations occurs:

- a calendar day (0:00 to 23:59) demonstrating at least 4 consecutive hours of headache of at least moderate severity
- a calendar day (0:00 to 23:59) demonstrating a headache of any duration that was treated with migraine- specific acute medications (triptans and ergot compounds)

The derivation logic is presented in [Appendix B](#).

The **monthly average number of days or hours** of efficacy variables (e.g., days of headache with at least moderate severity, migraine days, days of headache with any severity, total hours of headache with any severity, total hours of headache with at least moderate severity, days of use of any acute headache medications, days with nausea or vomiting, days with photophobia and phonophobia etc.) **during the 12-week period** after the 1st dose of study drug will be derived and normalized to **28** days equivalent using the following formula.

$$\frac{\sum \text{Days or hours of efficacy variable over the 12 week period}}{\sum \text{Days with assessments recorded in the eDiary for the 12 week period}} \times 28 \quad (1)$$

The **monthly number of days or hours** of efficacy variables **during a 4-week period** after each dose will be derived and normalized to **28** days equivalent using the following formula, where monthly data separated by each visit of study drug dosing will be used.

$$\frac{\sum \text{Days or hours of efficacy variable during the 4 week period}}{\sum \text{Days with assessments recorded in the eDiary for the 4 week period}} \times 28 \quad (2)$$

The **baseline values** will be calculated using all data collected in the run-in period.

$$\frac{\sum \text{Days or hours of efficacy variable during the run – in period}}{\sum \text{Days with assessments recorded in the eDiary for the run – in period}} \times 28 \quad (3)$$

The **percentage of reduction** in the monthly average number of an efficacy variable will be calculated as

$$\frac{\text{baseline value} - \text{postbaseline value}}{\text{baseline value}} \times 100\% \quad (4)$$

where the baseline value is calculated by formula (3) and the postbaseline value in the equation is calculated by formula (1) for the variables **during the 12-week period** or by formula (2) for the variables **during the 4-week period** after each dose for months 1, 2 and 3.

The **baseline values** for calculating the change from baseline of the weekly number of days of the efficacy variables will use all data collected in the run-in period and be calculated as

$$\frac{\sum \text{Days of efficacy variable during the run – in period}}{\sum \text{Days with assessments recorded in the eDiary for the run – in period}} \times 7 \quad (5)$$

The **weekly number of days** of efficacy variables (e.g., days of headache with at least moderate severity, migraine days) for each week during the 4-week period after the 1st dose of study drug will be derived and normalized to **7** days equivalent using the following formula.

$$\frac{\sum \text{Days or hours of efficacy variable during the 7 days period}}{\sum \text{Days with assessments recorded in the eDiary for the 7 days period}} \times 7 \quad (6)$$

The mITT analysis sets will be used for all efficacy analyses. Summaries will be presented by treatment group as randomized, unless otherwise noted. For the double-blind treatment period, summaries will be presented for the following treatment groups: placebo, fremanezumab quarterly, and fremanezumab monthly. For the open-label treatment period, summaries will be

presented by migraine classification (ie, CM, EM, and all), double-blind treatment group (ie, placebo, fremanezumab 675 mg/placebo/placebo, fremanezumab 675/225/225 mg, fremanezumab 225/225/225 mg, all fremanezumab), and overall (ie, total). Descriptive statistics for all efficacy data will be presented by month (or week) and over 12-week period for the double-blind period and the open-label period.

The primary and secondary endpoints analysis listed in Section 6.2.1 and Section 6.3 will be repeated for the per-protocol analysis set.

6.2. Primary Efficacy Endpoint and Analysis

6.2.1. Definition

The primary efficacy endpoint is the mean change from baseline (28-day run-in period) in the monthly average number of migraine days during the 12-week period after the 1st dose of fremanezumab.

6.2.2. Primary Efficacy Analysis

The hypothesis testing for the primary analysis is:

$$H_o : \delta_1 = \delta_2 \quad vs \quad H_a : \delta_1 \neq \delta_2$$

where δ_1 and δ_2 are the estimates of mean change from baseline in the monthly average number of migraine days for the fremanezumab treatment group and the placebo group respectively. The estimated difference of fremanezumab monthly dose versus the placebo and fremanezumab quarterly dose versus the placebo will be tested following the pre-specified fixed sequence as described in Section 7.

The primary efficacy endpoint will be analyzed using an analysis of covariance (ANCOVA) method. The model will include treatment, gender, region, special group of treatment failure (Yes or No), migraine classification (ie, CM or EM), and treatment-by-migraine classification interaction as fixed effects, and baseline number of migraine days and years since onset of migraines as covariates. The stratification factors (as randomized) will be used in the model. The treatment comparison between each fremanezumab treatment group (monthly dose and quarterly dose) and placebo for monthly average migraine days will be conducted under this model using the estimate statement. Ninety-five percent confidence intervals (CIs) will be constructed for the least square (LS) means differences between each fremanezumab treatment group (monthly dose and quarterly dose) and placebo.

Note: Special treatment failure group defined as patients who must have had inadequate response to valproic acid. In addition, patients in the special treatment failure group must have had inadequate response to 2 to 3 other classes of migraine preventive medications as defined in Appendix H of the protocol.

Type I error will be controlled for treatment comparisons by using Hochberg's method (see Section 7).

The following sample SAS code pertains to the primary analysis.

```
ODS OUTPUT DIFFS=XXX LSMEANS=XXX TESTS3=XXX;
```

```

PROC MIXED DATA=XXX;
    CLASS TREAT GENDER REGION TRTFAIL MIGCLASS;
    MODEL CHG=BASE YOD TREAT GENDER REGION TRTFAIL MIGCLASS
    TREAT*MIGCLASS/S;
    LSMEANS TREAT/PDIFF CL ALPHA=0.05;
RUN;

```

6.2.3. Sensitivity Analysis

6.2.3.1. MMRM Analysis

Sensitivity analysis will be performed using a mixed-effects model repeated measures (MMRM) analysis model to estimate the mean change from baseline in the monthly average of migraine days for the overall 3 months double-blind treatment period and by each month to support the primary analysis.

Each patient's monthly number of migraine days during the 4-week period will be calculated by formula (2) in Section 6.1. If a patient is early terminated or has intermittent missing days and has fewer than 10 days of electronic headache diary entries for a month, that month's value will be considered as missing as described in Section 4.3.

The MMRM model will include treatment, gender, region, special group of treatment failure (Yes or No), migraine classification (ie, CM or EM), month, treatment-by-migraine classification interaction, treatment-by-month interaction, and treatment-by-migraine classification-by-month interaction as fixed effects, baseline value and years since onset of migraines as covariates, and patient in the repeated statement as a random effect. The stratification factors (as randomized) will be used in the model. The unconstructed covariance structure will be used for the repeated observations within a patient. The treatment comparison between each fremanezumab treatment group (monthly dose and quarterly dose) and placebo for monthly average migraine days will be conducted under this model using the estimate statement. Ninety-five percent CIs will be constructed for the LS means differences between each fremanezumab treatment group (monthly dose and quarterly dose) and placebo. Note: Special treatment failure group defined as patients who must have had inadequate response to valproic acid. In addition, patients in the special treatment failure group must have had inadequate response to 2 to 3 other classes of migraine preventive medications as defined in Appendix H of the protocol.

The following SAS code pertains to the MMRM analysis:

```

ODS OUTPUT DIFFS=XXX LSMEANS=XXX TESTS3=XXX;
PROC MIXED DATA=XXX METHOD=REML;
    CLASS USUBJID TREAT GENDER REGION TRTFAIL MIGCLASS
    MONTH;
    MODEL CHG=BASE YOD TREAT GENDER REGION TRTFAIL MIGCLASS
    MONTH TREAT*MIGCLASS TREAT*MONTH
    TREAT*MIGCLASS*MONTH/S;

```

Statistical Analysis Plan

```
REPEATED MONTH / SUBJECT=USUBJID TYPE=UN R;
LSMEANS TREAT TREAT*MONTH/PDIFF CL ALPHA=0.05;
RUN;
```

This sensitivity analysis will be performed on the mITT analysis set.

6.2.3.2. Analysis with Multiple Imputation Method

Sensitivity analysis will be performed by imputing missing migraine days of months 1-3 using multiple imputation method. The data will be processed by the following steps.

- If a patient has partial electronic headache diary data (ie, <28 days) for a month, that month’s value will be considered missing before the MI procedure.
- For the patients in the fremanezumab treatment group who are early terminated with reasons of adverse event or lack of efficacy, they will be assigned to placebo group so their missing values will be imputed using data from the placebo treated patients
- Run SAS PROC MI procedure to create 100 complete datasets.

The following SAS code pertains to the MI analysis:

```
PROC MI DATA=XXX SEED=SEED OUT=MI_OUT NIMPUTE=100
MAXIMUM=. . . . . 28 28 28 MINIMUM=. . . . . 0 0 0;
CLASS TREAT GENDER REGION TRTFAIL MIGCLASS;
FCS REG (AVALMI1=TREAT GENDER REGION TRTFAIL MIGCLASS
BASE YOD/DETAILS) NBITER=100;
FCS REG (AVALMI2=TREAT GENDER REGION TRTFAIL MIGCLASS
BASE YOD AVALMI1/DETAILS) NBITER=100;
FCS REG (AVALMI3=TREAT GENDER REGION TRTFAIL MIGCLASS
BASE YOD AVALMI1 AVALMI2/DETAILS) NBITER=100;
VAR TREAT GENDER REGION TRTFAIL MIGCLASS YOD BASE
AVALMI1 AVALMI2 AVALMI3;
RUN;
```

- Within each imputed data set, for a patient who has partial, say X ($X < 28$) days , electronic headache diary data in a month, the monthly value will be replaced by
- $\sum(\text{observed days}) + (28 - X) * \text{imputed value} / 28$
- The monthly average number of migraine days *during the 12-week double-blind period* after the 1st dose of study drug will be the average of month 1, month 2 and month 3 values.

Each dataset will be analyzed using the same ANCOVA model as described in Section 6.2.2. The LS means and standard errors from each analysis will be output to a SAS data set. SAS MIANALYZE procedure will be used to generate the final LS means (\pm SE) for the treatment groups and the treatment differences (fremanezumab - placebo) as well as p-values associated with treatment differences. Ninety-five percent CIs for the LS means differences between each

Statistical Analysis Plan

fremanezumab treatment group (monthly dose and quarterly dose) and placebo will be constructed.

```
ODS OUTPUT DIFFS=MIXED_OUT;  
PROC MIXED DATA=UPDATED_MI_OUT METHOD=REML;  
BY _IMPUTATION_;  
CLASS TREAT GENDER REGION TRTFAIL MIGCLASS;  
MODEL CHG=BASE YOD TREAT GENDER REGION TRTFAIL MIGCLASS  
TREAT*MIGCLASS;  
LSMEANS TREAT/DIFF;  
RUN;
```

The output dataset from the above SAS code will contain the estimate of the mean difference and the standard error of the estimate from each of the 100 datasets. SAS procedure, PROC MIANALYZE, will be used to generate an overall p-value and 95% CI for the treatment difference. The following SAS code may be used.

```
ODS OUTPUT PARAMETERESTIMATES=PARMEST;  
PROC MIANALYZE DATA=MIXED_OUT ALPHA=0-.05 THETA0=0;  
BY TRTN;  
MODELEFFECTS ESTIMATE;  
STDERR=STDERR;  
RUN;
```

This sensitivity analysis will be performed on the ITT analysis set.

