4.3. Handling Withdrawals and Missing Data

If a patient has ≥ 10 days of electronic headache diary data after 1st dose of the study drug, his/her monthly average number of days/hours of efficacy variables *during the 12-week period* or monthly number of days/hours of efficacy variables *during the 4-week period* will be prorated to 28 days.

Multiple imputation (MI) method will be applied on the primary variable as sensitivity analyses. The methods will be described in detail in Section 6.2.3.

A patient's monthly number of days/hours of efficacy variables *during the 4-week period* after each dose of study drug will be calculated for months 1, 2, and 3. If a patient has missing diary days when calculating the monthly variables, the following method will be used to handle the missing data.

- If a patient has ≥ 10 days of electronic headache diary data for a month, the monthly number of days/hours of efficacy variables will be prorated to 28 days for that month.
- If a patient has < 10 days of electronic headache diary data for a month, the monthly number of days/hours of efficacy variables will be considered as missing.

The weekly number of headache days of at least moderate severity and migraine days will be calculated for the patients' 1st 28 calendar days of diary data after the 1st dose of study drug. Each week is defined as 7 calendar days counted from the 1st dose date. If a patient has missing diary days when calculating the weekly variables, the following method will be used to handle the missing data.

- If the patient has ≥ 3 days of electronic headache diary data for a week, the weekly number of days of efficacy variables will be prorated to 7 days for that week.
- If the patient has < 3 days of electronic headache diary data for a week, the weekly number of days of efficacy variables will be considered as missing for that week.

For the HIT-6 ([Appendix C](#)), if 1 or more items are missing then the total score is missing. The missing questionnaire items handling for the MSQOL questionnaire ([Appendix E](#)) is discussed in [Appendix F](#).

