4.4. Study Days and Visits

Study days are numbered relative to the 1st day of study drug administration. The start of treatment (day 1) is defined as the date on which a patient takes the 1st dose of study drug, as recorded on the study drug administration case report form (CRF). Days will be numbered relative to treatment start (ie, ..., -2, -1, 1, 2, ...; with day 1 being the 1st day of study drug administration and day -1 being the day before the 1st day of study drug administration).

The 4-week (28-day) visit windows for the electronic headache diary based efficacy endpoints will be determined based on the actual dosing day. The run-in phase is defined as day -28 to -1

Statistical Analysis Plan

before the 1st injection on day 1. Treatment phase including month 1, 2, 3, 4, 5, and 6 is from the beginning of the 1st injection of study drug to visit 8/day 168 or the end of treatment visit. The 6-month visit windows are separated by each dosing date/time. Month 1 is from the date/time of the 1st dose of study drug administration on day 1 to the date/time just before the 2nd dose. Month 2 is from the date/time of the 2nd dose to the date/time just before the 3rd dose. Month 3 is from the date/time of the 3rd dose to the date/time just before the 4th dose. Month 4 is from the date/time of the 4th dose to the date/time just before the 5th dose. Month 5 is from the date/time of the 5th dose to the date/time just before the 6th dose. Month 6 is from the date/time of the 6th dose to the end of treatment on day 168 approximately.

Throughout this document, all by month efficacy summaries for the headache data will refer to these visit windows.

The weekly (7-day) windows for calculating the weekly efficacy endpoints for the first 28 days will be determined based on the 1st dosing day. The first week is from day 1 to day 7, the second week is from day 8 to day 14, the third week is from day 15 to day 21, and the fourth week is from day 22 to day 28. Only the days between the first and the second dose will be included.

For all other by-visit summaries, if there are multiple assessments at a postbaseline visit then the last non-missing assessment at that visit will be used for the summary. This includes assessments at the scheduled and unscheduled visits.

For patients who withdraw from the study, their safety data at the early termination visit will be excluded from the by-visit summaries but will be included in the last assessment summaries.

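### The multiple-imputation sensitivity analysis draws unrecorded diary days without conditioning on the same month's recorded days, so its standard errors are mildly too small

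*SAP*

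**What the plan says.** The steps in SAP 6.2.3.2 are:

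- The trigger is worded "If a patient has partial electronic headache diary data (ie, <28 days) for a month", and the consequence is that "that month’s value will be considered missing before the MI procedure".
- Active-arm patients who stop for an adverse event or lack of efficacy are moved to the placebo group for imputation.
- The next step reads: "Run SAS PROC MI procedure to create 100 complete datasets". The month-1 statement begins "FCS REG (AVALMI1=TREAT GENDER REGION TRTFAIL MIGCLASS" and adds baseline migraine days and years since onset. Month 2 adds month 1, and month 3 adds months 1 and 2. No statement uses a later month.
- For a patient with X < 28 days of "electronic headache diary data in a month, the monthly value will be replaced by" the recorded migraine days plus (28 − X)/28 of the imputed monthly value.
- The average of the three months goes into the primary ANCOVA model, and PROC MIANALYZE pools the results on the ITT set.

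Elsewhere the threshold is 10 days. Under SAP 4.3, with fewer than 10 "days of electronic headache diary data for a month, the monthly number of days/hours of efficacy variables will be considered as missing". The MMRM (SAP 6.2.3.1) follows that rule. SAP 4.4 runs month 1 from the first dose "to the date/time just before the 2nd dose", and later months likewise. Protocol Table 2 allows ±3 days at the second, third and fourth dosing visits.

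**The concern.** Three features act together.

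- The 28-day trigger makes partial months common, and it catches months that have no missing diary day at all.
- The unrecorded part of a partial month is drawn around a model mean given baseline and, for months 2 and 3, earlier months. It is not drawn around the patient's level as shown by the other days of the same month.
- The month models are ordered as for monotone dropout, but the 28-day trigger produces scattered gaps, so observed later months go unused.

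A completed month therefore mixes the patient's own level with a draw independent of how far that month departs from the model. Such values vary too little between patients, and the within-imputation variance is too small. The between-imputation term does not make up the difference. At stake is the width of the interval in the only planned ITT analysis of the primary endpoint, which is also the one that imputes adverse-event and lack-of-efficacy dropouts from placebo.

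**Working it through.** **Plan's own figures.** SAP 6.2.3.2 states no number. The sample size in SAP 2.4 reproduces: 2 × (1.96 + 1.2816)² × 6²/1.8² = 233.5, so 234 per group (235 with the t distribution); 235/0.88 = 267.05, so 268 per group and 804 in all.

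**How the replacement formula behaves**

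- 27 recorded days, 20 with migraine, imputed month 8: 20 + 1 × 8/28 = 20.29.
- 20 recorded days, 14 with migraine, imputed month 6: 14 + 8 × 6/28 = 15.71.

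The recorded days dominate. In the second case, though, the patient had migraine on 70% of recorded days and receives 6/28 = 21% on the others.

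**How often a month is partial.** If days are completed independently at rate q (an assumption), P(28 of 28) = q^28. That is 24% at q = 0.95 and 5.2% at 0.90 (42 of 804). It is 0.03% at 0.75, the compliance floor in Protocol 6.1. Separately, if the second dose falls uniformly on days 25 to 31 (also assumed), 3/7 = 43% of fully recorded first months have fewer than 28 days.

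**Why the standard error is too small.** Take one arm and one month. Let d be the patient's deviation from the imputation mean, with variance τ². Let c be the share of complete months, p = 1 − c, and f the recorded fraction of a partial month. Day-to-day noise is ignored. A partial month becomes f·d + (1 − f)·e, with e an independent draw. In units of τ²/n:

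- true variance = c + 2p(1 − f) + p²(1 − f)²/c + p·f²
- Rubin variance = c + p[f² + 2(1 − f)²] + p²(1 − f)²/c
- shortfall = 2p·f(1 − f)

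The shortfall vanishes for a wholly missing month (f = 0) and for a complete one (f = 1). Only partial months cause it. With f = (q − c)/p:

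- q = 0.95: c = 0.238, p = 0.762, f = 0.934. True 1.014, Rubin 0.920, SE ratio √(0.920/1.014) = 0.95.
- q = 0.90: c = 0.052, p = 0.948, f = 0.894. True 1.202, Rubin 1.023, SE ratio √(1.023/1.202) = 0.92.

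Ignoring day-to-day noise tends to overstate the effect.

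**Simulation with the SAP replacement formula.** Mean Rubin SE divided by the empirical SD, relative to the same ratio with full data:

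- 235 per arm, 500 runs: about 0.96 at 95% daily completion and 0.92 to 0.94 at 90%. Prorating stayed at about 1.00.
- 268 per arm, 600 runs: 0.96 to 0.98 at 95% and 0.92 to 0.94 at 90%.

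A further set fixed the share of complete months directly (268 per arm, 1,200 runs, 20 imputations):

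| Complete months | Days in partial months | Full data | SAP rule | Prorated | SAP ÷ full |
|---|---|---|---|---|---|
| 90% | 22–27 | 0.97 | 0.96 | 0.97 | 0.99 |
| 60% | 22–27 | 1.02 | 0.98 | 1.01 | 0.96 |
| 30% | 22–27 | 1.02 | 0.95 | 1.02 | 0.93 |
| 30%, clustered by patient | 22–27 | 1.02 | 0.97 | 1.02 | 0.95 |
| 30% | 10–27 | 1.02 | 0.87 | 1.02 | 0.85 |
| 30%, clustered by patient | 10–27 | 1.02 | 0.91 | 1.03 | 0.89 |

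This last set left out the placebo-based step and most covariates. The Monte Carlo error of an SD from 500 runs is about 1/√1000 = 3%, so only ratios against a full-data control are used here.

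**Effect on coverage** (normal approximation, 2Φ(1.96r) − 1): r = 0.96 gives 94.0%, and r = 0.92 gives 92.9%.

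**The case against.** A reader who stops at the 28-day trigger might infer that the patient's recorded days are thrown away, or that the imputed part has nothing to do with the patient. The SAP supports neither reading. The replacement formula restores every recorded day, all three models contain the patient's baseline, months 2 and 3 use earlier months, and pooling adds between-imputation variance.

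The size is also uncertain. No completion rate is given. The 75% in Protocol 6.1 is a monitored minimum, not an expectation; late entry is allowed for up to 48 hours; and inclusion requires 24 run-in diary days. If completion varies between patients (beta distributed, assumed), complete months rise to 61–74% at 95% average completion and 36–55% at 90%.

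Nor would the planned effect change its status. The planned SE is 6 × √(2/235) = 0.554, so z = 1.8/0.554 = 3.25. An SE understated by 8% would report 3.25/0.92 = 3.53. Both are clearly significant.

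Finally, a blanket 10-day rule would do harm. An active-arm patient who stops for an adverse event on day 12 of a month would have that month prorated from on-treatment days, which removes the placebo-based imputation just where it matters. A sensitivity analysis may also reasonably depart from the proration used elsewhere.

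All of this stands. It limits the size of the point and shapes the fix, but it does not supply the missing conditioning on the same month's days.

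**Conclusion.** The point holds as a mild, conditional defect. Rubin's SE in SAP 6.2.3.2 is understated by about 3 to 4% at 95% daily completion and 6 to 8% at 90%. The shortfall grows as completion falls: about 11 to 15% in the simulated case with 30% complete months and 10 to 27 recorded days in the rest. With 80 to 90% of months complete it is about 1 to 2%. All of these figures rest on assumed completion patterns.

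The main cause is the lack of conditioning on same-month days. Letting each model use the other months recovers only about 0.5 to 1.5 percentage points of the SE ratio.

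One might infer that the trial's main result is at risk. It is not: the primary ANCOVA prorates recorded days over the 12 weeks, the MMRM uses the 10-day rule, and the testing procedure in SAP 7 does not include this analysis.

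**What to change.** In SAP 6.2.3.2:

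1. For patients still in the double-blind period, treat a month with at least 10 diary days as observed and prorate it with formula (2) of SAP 6.1. Judge completeness against the actual dose-to-dose window. Set a month to missing for imputation only when it has fewer than 10 days.
2. For patients who terminate early, keep the present formula (recorded days plus imputed remainder) for the dropout month, so that adverse-event and lack-of-efficacy dropouts are still imputed from placebo.
3. Let each FCS REG statement include the other two months.

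The cost is a few lines of SAP text and code before the first interim lock, and slightly wider intervals in this analysis. No data collection changes.
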